#### **Non-hematologic**

- Grade 3 or greater nausea, vomiting, or diarrhea if persistent despite optimal antiemetic or anti-diarrheal therapy.

- Grade 3 or greater increase in transaminases lasting > 5 days.
- Grade 3 or greater fatigue persisting > 7 days in the absence of any other underlying cause.
- Any other Grade 3 or greater non-hematologic toxicity (except fatigue as noted above) considered clinically significant by the investigator.
- Toxicity of any grade resulting in dose delay of more than 7 days.
- Toxicity resulting in study drug discontinuation prior to the completion of Cycle 1.

#### **5.2.1.2. Phase 2a: Monitoring for Toxicity in Phase 2a**

Patients will be monitored for toxicity throughout Phase 2a. For the purposes of this protocol, toxicity is defined as any Grade 3 or higher adverse event (AE) and/or any clinically significant AE (refer to [Table 8](#)). Patients experiencing a toxicity may be considered for a dose interruption or reduction. Enrollment in a cohort may be suspended at any time depending on the overall toxicity profile within that cohort, pending a review by the Study Committee, and consideration will be given to discontinuing enrollment in that cohort or providing a global dose reduction for that cohort.

Physicians should monitor for infections and clinically significant decreases in leukocyte counts (e.g., ALC, ANC) and should consider holding cerdulatinib and/or dose modifications per [Section 5.2.1.3](#) if clinically significant toxicity occurs. Also see [Section 10.1.3](#), Adverse Events that May Indicate Potential Drug Toxicity.

#### **5.2.1.3. Dose Modifications for Cerdulatinib**

##### **5.2.1.3.1. Dose Modifications to Cerdulatinib During Phase 2a**

Dose reductions and interruptions are permitted during all cycles. Guidelines for dose modifications are provided in [Table 8](#).

In general, for Grade 1 or 2 adverse events that are medically manageable, the Investigator is encouraged to continue dosing and institute standard of care support or hold dosing and institute standard of care support, and then restart dosing at the same dose after the event has resolved to baseline. Specific guidance for management of Grade 1 and 2 diarrhea and nausea and vomiting is provided in [Sections 5.2.1.5](#) and [5.2.1.6](#).

For adverse events  $\geq$  Grade 3, rather than dose interruption or dose reduction, the Investigator is encouraged to hold dosing and institute standard of care support, and then restart dosing at the same dose after the event has resolved to baseline, as clinically appropriate. [Table 8](#) provides further guidance on Grade 3 toxicities. A dose interruption does not necessitate a subsequent dose reduction. In the case of a dose interruption, once the toxicity has resolved to Grade < 2 or

baseline, the Investigator should use clinical judgement when deciding to restart the patient at the same dose level or at a reduced dose.

Patients may be dose-reduced in increments from their starting dose, one level at a time, to the lowest dose level of 15 mg BID. A patient experiencing a toxicity at 15 mg BID should be discontinued from cerdulatinib and removed from the study (after completing the 30 Day Post-Last Treatment Visit in Section 7.3.2.2).

Patients who experience dose interruptions > 28 days in duration should be permanently discontinued from cerdulatinib therapy (after completing the 30 Day Post-Last Treatment Visit in Section 7.3.2.2). Exceptions that would allow such patients to continue study treatment may be allowed at the discretion of the Investigator based upon clinical judgement and with Sponsor Medical Monitor approval.

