      - If in any cohort 2 or more of the first 3 patients or  $\geq 33\%$  of patients in a cohort develop DLT, dose escalation will cease, and that dose level will be declared intolerable. The prior dose level will either be declared the MTD, and the cohort may be expanded to as many as 6 patients if fewer than 6 patients had been treated previously at that dose level in order to further characterize the PK and PD at that level.
- The study is currently in Phase 2a: Exploratory, consisting of 6 cohorts, each defined by cancer type and prior therapy
  - Under Amendment 7, the starting dose of orally administered cerdulatinib is either 30, 25, or 20 mg BID. Subsequent de-escalations to 25, 20, and then 15 mg BID are permitted. A patient who has been de-escalated may be re-escalated at the discretion of the Investigator based upon clinical judgement and with Sponsor Medical Monitor approval per the Dose Modification Guidelines for Phase 2a (Section 5.2.1.3).
  - The 6 cohorts are defined below:
    - **Cohort 1:** Patients with follicular lymphoma Grade 1 to 3A who have received  $\geq 1$  prior treatment regimen.
    - **Cohort 2:** Patients with FL Grade 1 to 3A who have received  $\geq 1$  prior treatment regimen. In addition to receiving cerdulatinib, this cohort will also receive rituximab IV at 375 mg/m^2 during Cycle 1 on Days 1, 8, 15, and 22 and during Cycles 4, 6, 8, and 10 on Day 1 only.

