### 5.1.3. **Phase 2a Cerdulatinib Dosing**

Following confirmation of eligibility, patients will receive oral cerdulatinib at a starting dose of 30, 25, or 20 mg BID. Every effort should be made to administer study drug at the same time each day. The drug will be administered in cycles of 28 days with no days off therapy between cycles.

In the event of toxicity (see Section 5.2.1 for the definition of *toxicity*), dosing may be interrupted at the discretion of the Investigator until sufficient resolution of the toxicity is attained and then restarted at a lower dose level (dose modifications to cerdulatinib are summarized in Table 8). The lowest dose of cerdulatinib that may be administered is 15 mg BID.

Dosing information for rituximab is described in Section 6.2 (for Cohort 2, the combination cohort of cerdulatinib and rituximab).

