**Table 8: Guidelines for Dose Reductions for Cerdulatinib**

Toxicity	Occurrence	Action 
Hematologic Grade 3 or 4 febrile neutropenia Grade 4 neutropenia for $\geq 7$ days, or Grade 4 thrombocytopenia	1 st	Hold study drug. Once toxicity has resolved to Grade < 2 or baseline, may restart cerdulatinib at the next lower dose level.
	2 nd	Hold study drug. Once toxicity has resolved to Grade < 2 or baseline, may restart cerdulatinib at two dose levels below the starting dose.
	3 rd	Discontinue cerdulatinib
Gastrointestinal Grade 3 or 4 nausea, vomiting, or diarrhea if persistent despite optimal antiemetic or antidiarrheal therapy Grade 3 or greater increase in ALT/AST, total bilirubin	1 st	Hold study drug. Once toxicity has resolved to Grade < 2 or baseline, may restart cerdulatinib at the next lower dose level.
	2 nd	Hold study drug. Once toxicity has resolved to Grade < 2 or baseline, may restart cerdulatinib at two dose levels below the starting dose.
	3 rd	Discontinue cerdulatinib
Other Any other related Grade 3 or 4 non-laboratory toxicity Any other related Grade 3 or 4 laboratory toxicity considered clinically significant by the Investigator (e.g., symptomatic) (Do not dose reduce or hold study drug for asymptomatic amylase or lipase elevations  )	1 st	Hold study drug. Once toxicity has resolved to Grade < 2 or baseline, may restart cerdulatinib at the next lower dose level.
	2 nd	Hold study drug. Once toxicity has resolved to Grade < 2 or baseline, may restart cerdulatinib at two dose levels below the starting dose.
	3 rd	Discontinue cerdulatinib

AE = Adverse event; ALT = Alanine aminotransferase; AST = Aspartate aminotransferase

Note: Grading is NCI CTCAE v5.0.

 Do not dose reduce below 15 mg BID. At 15 mg BID, if any toxicity (Grade 3 or greater AE and/or any clinically significant AE) occurs, discontinue cerdulatinib (and rituximab for the combination cohort of cerdulatinib and rituximab) after completing the 30 Day Post-Last Treatment Visit in Section 7.3.2.2.

  $\geq$  Grade 3 asymptomatic elevations in amylase and lipase have been observed in this study without clinical pancreatitis.

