#### **5.2.1.5. Management of Diarrhea**

Grade 1 or 2: The patient may continue receiving study drug. Institute anti-diarrheal treatment (e.g., loperamide [Imodium®] or diphenoxylate/atropine [Lomotil®]) and consider BRAT (bananas, rice, applesauce, and toast) diet. Persistent Grade 2 diarrhea despite optimal therapy may be managed with dose reduction.

Grade ≥ 3: Hold study drug. Once toxicity has resolved to Grade < 2 or baseline, restart cerdulatinib at the same dose level or at the next lower dose level.

Also, if clinically indicated, the patient should be assessed for *C. difficile* infection.

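### Phase 2a restart guidance after Grade 3 or higher toxicity differs between protocol sections, and Table 8's second-occurrence action cannot be carried out for a 20 mg BID starter who is at 20 mg BID

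*Protocol*

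**What the plan says.** All references are to the protocol unless the SAP is named.

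- **Starting doses and levels.** Under Section 5.1.3, "patients will receive oral cerdulatinib at a starting dose of 30, 25, or 20 mg BID". The Synopsis adds that "Subsequent de-escalations to 25, 20, and then 15 mg BID are permitted", and Section 5.1.3 sets the floor: "The lowest dose of cerdulatinib that may be administered is 15 mg BID".
- **Section 5.2.1.3.1.** For Grade 3 or higher events the investigator is encouraged to hold drug, give supportive care and "restart dosing at the same dose after the event has resolved to baseline, as clinically appropriate". The section then refers to Table 8 for further guidance, says an interruption need not be followed by a reduction, and leaves same or reduced dose to clinical judgement once the event is below Grade 2 or at baseline. It also says that reductions go down by single levels.
- **Table 8.** For each toxicity group the first-occurrence entry is to hold drug and, on recovery, "may restart cerdulatinib at the next lower dose level". The second-occurrence entry is "may restart cerdulatinib at two dose levels below the starting dose". The third is discontinuation. Footnote 1, attached to the action column, forbids going below 15 mg BID and requires discontinuation for any toxicity at that dose.
- **Sections 5.2.1.5 and 5.2.1.6.** For Grade 3 or higher diarrhea, nausea or vomiting: "restart cerdulatinib at the same dose level or at the next lower dose level".
- **Sections 5.1.1 and 5.1.3.** Both mention only a lower level. Section 5.1.3 allows interruption "until sufficient resolution of the toxicity is attained and then restarted at a lower dose level" and points to Table 8; Section 5.1.1 points to Section 5.2.

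**The concern.** Section 5.2.1.2 defines toxicity in Phase 2a to include every Grade 3 or higher adverse event, so these sections apply to overlapping sets of events. They do not list the same restart options, and no section says which prevails. Two patients with the same starting dose and the same event could therefore be restarted at different doses because different pages were consulted, not because a clinical judgement differed. One Table 8 entry also names a dose level that does not exist for one of the three starting doses.

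The first thing at stake is the management of serious toxicity. The second is the exposure reporting in SAP Section 7.9.1 (Treatment Exposure and Compliance), which tabulates dose reductions, interruptions and discontinuations and computes relative dose intensity against the initial assigned dose.

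**Working it through.** No sample size, power or error rate is involved. The check applies each instruction to the protocol's own dose levels.

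**Inputs.** Levels are 30 > 25 > 20 > 15 mg BID (Synopsis; floor in Section 5.1.3 and Table 8 footnote 1). Starting doses are 30, 25 and 20 mg BID (Section 5.1.3).

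**First Grade 3 or higher event, patient at the starting dose (mg BID):**

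| Start | 5.2.1.3.1, encouraged | 5.2.1.3.1, judgement sentence | Table 8 | 5.2.1.5 / 5.2.1.6 (GI) | 5.1.1 / 5.1.3 |
|---|---|---|---|---|---|
| 30 | 30 | 30 or lower | 25 | 30 or 25 | a lower level |
| 25 | 25 | 25 or lower | 20 | 25 or 20 | a lower level |
| 20 | 20 | 20 or lower | 15 | 20 or 15 | 15 |

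A Grade 3 diarrhea that persists in spite of best treatment falls under every column. Diarrhea that does not meet that qualifier falls outside Table 8's gastrointestinal row, so the overlap there is partial.

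**Second occurrence under Table 8 (starting level minus two levels):**

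- Start 30: 30 → 25 → 20, so 20 mg BID.
- Start 25: 25 → 20 → 15, so 15 mg BID.
- Start 20: 20 → 15 → none. Only one level lies below 20.

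What this means depends on the dose at the second event:

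- *20 mg starter now at 15.* Footnote 1 and Section 5.2.1.3.1 both give discontinuation, so there is no gap.
- *20 mg starter still at 20* (restarted at the same dose under 5.2.1.3.1, 5.2.1.5 or 5.2.1.6) *or back at 20* (re-escalated under 5.2.1.3.2). The entry cannot be carried out. Footnote 1 bars the reduction it calls for but states no replacement action.
- *30 or 25 mg starter still at the starting dose.* The entry means a two-level drop (30 to 20, or 25 to 15), whereas Section 5.2.1.3.1 says reductions go by single levels.

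**Recovery standard.** Within Section 5.2.1.3.1, one sentence requires return to baseline and a later one accepts below Grade 2 or baseline. Table 8 and Sections 5.2.1.5 and 5.2.1.6 use the second form. Sections 5.1.1 and 5.1.3 ask only for sufficient resolution.

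**Hold versus interruption.** Section 5.2.1.3.1 recommends holding drug in preference to interrupting it, without saying how the two differ. SAP Section 7.9.1 counts dose interruptions, so the distinction matters for the table.

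**Effect on relative dose intensity.** The SAP divides actual by initially assigned mg/day. For fully adherent days after restart, a same-dose restart gives 100%. A restart one level lower gives:

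- Start 30: 50/60 = 83.3%
- Start 25: 40/50 = 80.0%
- Start 20: 30/40 = 75.0%

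These are values for post-restart days only. The reported figure averages over the whole treatment period, including days held, so the difference in a patient's summary would be smaller.

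**The case against.** The strongest reply is that this is guidance, deliberately flexible. Table 8 is titled as guidelines and uses permissive verbs; the same-dose sentence is an encouragement, qualified by clinical appropriateness; and the judgement sentence in Section 5.2.1.3.1, read with Sections 5.2.1.5 and 5.2.1.6, already admits either option. Sections 5.1.1 and 5.1.3 can be read as general pointers to the detailed guidance. The Amendment 9 entry in the summary of changes shows the sponsor softening Table 8 to agree with Section 5.2.1.3.1.

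Much of this stands. A reader might infer that the sections give flatly opposite orders; the permissive wording does not support that. Some variation between patients is intended. Flexibility still needs one list of options, however, and the pointers lead to a table that omits the option Section 5.2.1.3.1 encourages. Discretion does not supply a level below 15 mg BID.

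Two further readings go too far:

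- *That a 20 mg BID start has no usable second-occurrence rule.* Footnote 1 gives one for a patient who followed Table 8 down to 15 mg BID.
- *That inconsistent handling confounds a comparison of the three starting doses, or varies by site.* Section 3.1.2.2.1 says the doses may be explored, and no formal between-dose test is planned. Protocol Section 11.1.1 does foresee summaries by dose level, but they are descriptive. SAP Sections 7.1 and 7.9 present Phase 2a by cancer type, with selected safety summaries repeated for 30 mg BID starters. Nothing in the documents shows that sites handle events differently.

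**Conclusion.** The concern holds in a limited form: the restart guidance is wrong as written.

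- The sections list different restart options for overlapping events. For a first event the difference between same-dose and next-lower restart is one dose level from any starting dose.
- Section 5.2.1.3.1 states two recovery thresholds, leaves hold and interruption undistinguished, and has a single-level rule that Table 8's second-occurrence entry can break.
- That entry fails for 20 mg BID starters who are at 20 mg BID at the second event. The documents do not say how many patients this would be. It is a foreseeable path, because same-dose restart is encouraged and re-escalation is permitted.

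The consequences are for patient handling and for the descriptive summaries of reductions, interruptions and relative dose intensity. No sample-size figure, primary analysis or formal dose comparison changes. The conclusion assumes that the levels are exactly 30, 25, 20 and 15 mg BID, as the Synopsis lists them. No view is taken on which restart rule or dose is right.

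**What to change.** The sponsor's clinical team should reconcile Sections 5.1.1, 5.1.3, 5.2.1.3.1, 5.2.1.5 and 5.2.1.6 and Table 8 so that:

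- all list the same restart options, most simply by keeping them in one place that the other sections cite;
- one recovery standard applies throughout, and hold and interruption are either defined separately or treated as one term;
- the second-occurrence action can be carried out from each of the three starting doses, including for a patient still at or returned to 20 mg BID, and agrees with the rule on reduction steps.

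The clinical content is the sponsor's decision. Investigator discretion can remain, provided it is stated once. The cost is a protocol wording change or a site memo, with no new data, visits or patients.

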#### **5.2.1.3.2. Dose Re-escalations During Phase 2a**

In Phase 2a, a patient who has been dose reduced from their starting dose may be re-escalated incrementally to the next higher dose level at the discretion of the Investigator based upon clinical judgement and with Sponsor Medical Monitor approval. Dose re-escalation to the next higher dose level should occur at the start of the next cycle.

**Table 8: Guidelines for Dose Reductions for Cerdulatinib**

Toxicity	Occurrence	Action 
Hematologic Grade 3 or 4 febrile neutropenia Grade 4 neutropenia for $\geq 7$ days, or Grade 4 thrombocytopenia	1 st	Hold study drug. Once toxicity has resolved to Grade < 2 or baseline, may restart cerdulatinib at the next lower dose level.
	2 nd	Hold study drug. Once toxicity has resolved to Grade < 2 or baseline, may restart cerdulatinib at two dose levels below the starting dose.
	3 rd	Discontinue cerdulatinib
Gastrointestinal Grade 3 or 4 nausea, vomiting, or diarrhea if persistent despite optimal antiemetic or antidiarrheal therapy Grade 3 or greater increase in ALT/AST, total bilirubin	1 st	Hold study drug. Once toxicity has resolved to Grade < 2 or baseline, may restart cerdulatinib at the next lower dose level.
	2 nd	Hold study drug. Once toxicity has resolved to Grade < 2 or baseline, may restart cerdulatinib at two dose levels below the starting dose.
	3 rd	Discontinue cerdulatinib
Other Any other related Grade 3 or 4 non-laboratory toxicity Any other related Grade 3 or 4 laboratory toxicity considered clinically significant by the Investigator (e.g., symptomatic) (Do not dose reduce or hold study drug for asymptomatic amylase or lipase elevations  )	1 st	Hold study drug. Once toxicity has resolved to Grade < 2 or baseline, may restart cerdulatinib at the next lower dose level.
	2 nd	Hold study drug. Once toxicity has resolved to Grade < 2 or baseline, may restart cerdulatinib at two dose levels below the starting dose.
	3 rd	Discontinue cerdulatinib

AE = Adverse event; ALT = Alanine aminotransferase; AST = Aspartate aminotransferase

Note: Grading is NCI CTCAE v5.0.

 Do not dose reduce below 15 mg BID. At 15 mg BID, if any toxicity (Grade 3 or greater AE and/or any clinically significant AE) occurs, discontinue cerdulatinib (and rituximab for the combination cohort of cerdulatinib and rituximab) after completing the 30 Day Post-Last Treatment Visit in Section 7.3.2.2.

  $\geq$  Grade 3 asymptomatic elevations in amylase and lipase have been observed in this study without clinical pancreatitis.

#### 5.2.1.4. Management of Potential Epstein-Barr Virus Reactivation

EBV reactivation has been observed in connection with cerdulatinib administration and should be viewed as a potential adverse effect of treatment. For this reason, peripheral blood quantitative EBV polymerase chain reaction assay (PCR) has been added to the baseline assessment of subjects and should be performed post-baseline for any unexplained fevers if there is clinical suspicion of EBV reactivation.

If unexplained fever and increased EBV PCR raise clinical suspicion of EBV reactivation or infection, the investigator should take the following action \*:

1. Hold cerdulatinib dosing.
2. Continue monitoring the patient's EBV viral load with quantitative PCR per local standard of care (typically weekly).

3. Administer symptomatic treatment per local standard of care.
4. Consider therapy with rituximab at a dose of 375 mg/m^2 once weekly until normalization of the patient's viral load. Typically, one to four doses of rituximab are used [73, 74]. The use of rituximab does not require study discontinuation.
5. After symptoms resolve, resume cerdulatinib treatment at the same dose level or one dose level below the current dose level and continue monitoring the patient's EBV viral load with quantitative PCR per local standard of care (typically monthly).

\* Cerdulatinib dosing may continue while rituximab therapy is administered, with the Medical Monitor approval. For asymptomatic increased EBV PCR, consider treatment with rituximab (per local standard of care) and continuing cerdulatinib.

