Amendment 7: 06 March 2019 (Cont'd)	
 
○ HIV and hepatitis (EC #10): positive/negative status must be known, with additional testing required if a patient does not have documentation of prior negative hepatitis panel or negative HIV history for patients.
 
○ Removed the directive to administer cerdulatinib under fasting conditions; cerdulatinib may be administered with food (Section 5.1.1).
 
○ Peripheral blood quantitative EBV polymerase chain reaction assay (PCR) was added to the baseline assessment and should be performed post-baseline for any unexplained fevers if there is clinical suspicion of EBV reactivation (Section 5.2.1.4).
 
○ Guidance on the management of Grade 1 and 2 diarrhea, nausea and vomiting was added (Sections 5.2.1.5 and 5.2.1.6).
 
○ The guidelines for dose reductions for cerdulatinib were updated (Table 8).
 
● Clarified that rituximab is not provided by the Sponsor as it is considered standard of care (Section 5.3).
 
● Added collection of molecular/mutation profile if obtained as standard of care (Section 7.1.9.2).
 
● Clarified that patients may continue adjuvant hormonal therapy for prostate or breast cancer (Section 7.5.1).
 
● Immunosuppressive agents was removed as a prohibited medication group (Section 7.5.1).
 
● Restrictions on the administration of anti-emetic agents were removed (Section 7.5.2).
 
● Description of the Study Committee composition and function was revised to reflect current review practice (Section 7.6).
 
● Assessment of Safety (Section 10.0) was revised for clarity. No new information was added.
 
● For Cohort 1 iNHL patients only, whole blood sample collection for immune flow chemistry was removed from the protocol (Section 7.1.10.2 and Appendix 1).
 
● Whole blood sample collection (all patients) for isolation of cell-free tumor DNA (ctDNA) was added (Section 7.1.10.1 and Appendix 1).
 
● Post-dose vital signs assessments was removed from Cycle 2, Day 1 in the Schedule of Assessments (Appendix 1); a post-dose assessment was added in error to Cycle 2, Day 15.
 
● Medical Monitor changed to [REDACTED] Syneos Health (previously: [REDACTED] Medical Monitor, INC Research).
 
● Administrative Sections 12.0 – 16.0 were updated to align with company standard.
 
● Appendix 12 was removed. This appendix contained the methodology applicable to the Phase 1 portion of the study which is closed, but may be referenced in earlier versions of the protocol.
 

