#### 7.5.1. **Prohibited Medications/Procedures**

- Chemotherapy, radiation therapy, hormonal therapy or any investigational anti-neoplastic agent for the active treatment of cancer are prohibited. Patients may continue on adjuvant hormonal therapy for prostate or breast cancer, as long as there is no detectable disease at study entry.
- Systemic steroids, at doses greater than the equivalent of 20 mg prednisone daily, with the exception of intermittent use for the treatment of emesis, are prohibited. Steroid inhalers for medical conditions are permitted. Patients needing pulse corticosteroids for other medical conditions should be discussed with the Sponsor’s Medical Monitor.

- Nasal flu vaccine is prohibited because the nasal vaccine is a live, attenuated virus; however, flu injections, which are nonviable antigens, are permitted (see Section 7.5.2).

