7.8.1. Primary Efficacy Endpoint

Overall response rate (ORR) is defined as the proportion of subjects who achieve partial response (PR) or better as the best overall response (BOR) per Lugano criteria (Cheson, 2014, see appendix C) as assessed by the investigator. BOR is defined as the best response from treatment start to the data cutoff date (inclusive), disease progression (inclusive), or the start of new anti-cancer therapies (inclusive), whichever occurs first.

ORR will be calculated by cohort, and the associated 95% exact confidence interval (CI) will be estimated using the Clopper-Pearson method.

The primary endpoint of ORR may also be analyzed in additional subgroups of the efficacy analysis population as sensitivity analysis.

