7.8.2. Secondary Efficacy Endpoint

7.8.2.1. Progression free survival

Progression-free survival (PFS) is defined as the time from the start of study treatment to the first documentation of disease progression as assessed by investigator (see appendix C) or death from any cause, whichever occurs first.

Progression-free survival = (first documentation of disease progression or death – first dose date of study treatment + 1) /30.4375 in months.

PFS will be right censored for subjects who meet one of the following conditions: 1) no baseline disease assessments; 2) starting a new anti-cancer therapy before documented disease progression or death; 3) progression or death immediately after more than 6 months since the last disease assessment (or more than 12 months if beyond cycle 12); and alive without documented disease progression. The censoring convention follows the FDA guidance for Industry Clinical Trial Endpoints for the Approval of Cancer Drugs and Biologics (2018) and references within the guidance document. The censoring rules are summarized in Table 1.

Table 1. Date of Event or Censoring for PFS

Scenario	Date of PFS Event or Censoring	Outcome
Death or progression between the planned disease assessments	Date of death or first disease assessment showing PD, whichever occurs first	Event
Death before the first disease assessment	Date of death	Event
No baseline disease assessment	Date of first dose of study treatment	Censored
New anti-cancer treatment started	Date of last disease assessment prior to or on the date of new anti-cancer treatment	Censored
Death or progression immediately after missing more than 1 scheduled disease assessment ^[1]	Date of the last disease assessment before death or progression	Censored
Alive without documented disease progression	Date of last disease assessment	Censored

^[1] missing ≥ 6 months if in Cycle 1~12 or missing ≥ 12 months if beyond Cycle 12

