7.8.2.2. Duration of response

For responders (PR or better), duration of response (DOR) is defined as the time from the date of the earliest PR or better to the first documentation of disease progression or death from any cause, whichever occurs first. The censoring convention and analysis method of DOR will be the same as those for PFS in Section 7.8.2.1. DOR will be analyzed for subjects who achieved PR or better (i.e. responders only).

DOR = (first documentation of progression or death – the date of the earliest PR or better + 1) /30.4375 in months.

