If the start day of a subsequent anti-cancer therapy is missing, it will be assumed to be the first day of the month.

5. Cancer Diagnosis

If a cancer diagnosis date is partially missing, impute as follows:

- If both month and day are missing, the imputed value will be Jan 1
- If only day is missing, the imputed day will be the first day of the month
- If end date is completely missing, do not impute

6. Prior Therapy/Response to Prior Therapy

If the day of a prior therapy or response to prior therapy date is missing, set it to 15th of the month. Otherwise, do not impute.

B. Pathology subgroup of Peripheral T-cell Lymphoma (PTCL)

CSR TFL Column	Pathology in EDC
AITL/TFH	AITCL
	PTCL Angioimmunoblastic T-Cell Lymphoma (AITL)
	PTCL with T-follicular helper phenotype
NOS	PTCL (Peripheral T-Cell Lymphoma) -NOS
Others	ATLL
	ATLL
	ATLL, HTLV-1 associated
	CD4+ PTCL, skin only
	CD4+ PTCL, skin-only
	Cutaneous Gamma Delta
	Cutaneous gamma-delta T-cell Lymphoma
	G/D TCL, skin and LN+
	HTLV-1 ATLL
	Hepatosplenic T cell Lymphoma
	Hepatosplenic T-cell Lymphoma
	LGL*
	Monomorphic Epitheliotropic Intestinal T-Cell Lymphoma
	NK/T-cell
	PTCL Anaplastic Large Cell Lymphoma (ALCL) ALK Negative (-)
	Primary Cutaneous Gamma/Delta T-cell Lymphoma
	T-Cell Prolymphocytic Leukemia
	T-cell prolymphocytic leukemia
	aggressive epidermotropic CD8+ **
	gamma-delta T-cell lymphoma
hepatosplenic T Cell lymphoma	
hepatosplenic gamma-delta T cell lymphoma	

*LGL (large granular lymphocytic leukemia) was miscategorized as PTCL at study entry

**CTCL with aggressive epidermotropic CD8+ was miscategorized as PTCL at study entry

C. Lugano Criteria for Response Assessments in NHL (Protocol Amendment 9 Table A4-11).

Response and Site	PET-CT–Based Response	CT-Based Response

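### Does rituximab given for EBV reactivation count as new anti-cancer therapy when response is scored in the single-agent follicular lymphoma cohort?

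*Protocol*

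**What the plan says.** **EBV management.** Protocol 5.2.1.4 treats EBV reactivation as a possible adverse effect of cerdulatinib. Among the steps to consider is weekly rituximab at 375 mg/m², usually one to four doses. It adds: "The use of rituximab does not require study discontinuation". A footnote extends this to patients without symptoms: "For asymptomatic increased EBV PCR, consider treatment with rituximab (per local standard of care) and continuing cerdulatinib". The section names no cohort. Table 2 records under Amendment 7 that "Peripheral blood quantitative EBV polymerase chain reaction assay (PCR) was added to the baseline assessment". It does not date the rituximab step itself, and Amendment 8 later revised the EBV instructions.

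**Primary endpoint.** Under SAP 7.8.1, best overall response runs from treatment start to "data cutoff date (inclusive), disease progression (inclusive), or the start of new anti-cancer therapies (inclusive), whichever occurs first".

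**Time-to-event endpoints.** In SAP 7.8.2.1, Table 1 censors progression-free survival (PFS) when new anti-cancer treatment starts, at "Date of last disease assessment prior to or on the date of new anti-cancer treatment". Duration of response (DOR) follows: "The censoring convention and analysis method of DOR will be the same as those for PFS in Section 7.8.2.1".

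**Definition of the term.** None is given. Appendix A of the SAP deals only with an incomplete date: "If the start day of a subsequent anti-cancer therapy is missing, it will be assumed to be the first day of the month".

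**The concern.** The protocol's background sections (1.6.2 and 1.6.4) describe rituximab as approved and widely used in low-grade lymphoma, including as a single agent in FL. Section 5.0 says Cohort 1 receives cerdulatinib alone. If a Cohort 1 patient receives up to four weekly doses for EBV and only then shows a first partial or complete response, two readings are possible:

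- **By purpose.** The rituximab was supportive care, the window stays open, and the response counts towards single-agent ORR.
- **By drug.** An active anti-lymphoma antibody was started, the window closes, the response is not counted, and PFS is censored.

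The first reading could credit cerdulatinib with a response that rituximab helped to produce. The second could discard a genuine one. Response is investigator-assessed in an unblinded study, so a rule left unwritten could be settled after the responses are known. Cohort 1 also provides the only summarised estimate of single-agent activity in FL, because SAP Section 8 limits aggregate efficacy to FL in Cohorts 1 and 2 and peripheral T-cell lymphoma in Cohort 5.

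**Working it through.** **1. Can the sequence occur before the first scan?**
Cycles last 28 days and the first scheduled on-treatment scan is at Cycle 3 Day 1 (Protocol Appendix 1), which is day 1 + 2 × 28 = 57. The scan footnote allows 7 days earlier, so day 50. Four weekly doses begun on day 28 end on day 28 + 3 × 7 = 49. The sequence is feasible, and could also occur before later scans.

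**2. Which patients are affected?**
The window in SAP 7.8.1 includes the day the new therapy starts, so a response documented on or before that day counts on both readings. An affected patient must be in Cohort 1 FL, have raised EBV, be given a drug that is only to be considered, have no earlier response, and respond afterwards. The documents give no count. Protocol 1.5 says Phase 1 responses typically came after 2 cycles, which suggests many would be documented early.

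**3. How large is the effect?**
Method: Clopper-Pearson, two-sided 95% (SAP 7.8.1). The lower limit is the 0.025 quantile of Beta(x, n−x+1); the upper limit is the 0.975 quantile of Beta(x+1, n−x).

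The plan's own figures first (Protocol Synopsis, Sample Size Considerations):

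| Case | Plan | Recomputed |
|---|---|---|
| 12/40 = 30% | 16.6 to 46.5% | 16.6 to 46.5% |
| 8/40 = 20% | 9.1 to 35.7% | 9.1 to 35.6% (rounding) |
| 1/20, upper limit | about 25% | 24.9% |

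Each reclassified responder moves ORR by 100/n points: 5.0 at n = 20, 2.5 at n = 40 and 2.0 at n = 50. Starting from 12/40, with the number reclassified assumed:

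| Reclassified | ORR | Exact 95% interval |
|---|---|---|
| 0 | 30.0% | 16.6 to 46.5% |
| 1 | 27.5% | 14.6 to 43.9% |
| 2 | 25.0% | 12.7 to 41.2% |
| 3 | 22.5% | 10.8 to 38.5% |

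The interval at 12/40 is 46.5 − 16.6 = 29.9 points wide. One patient shifts the estimate by about a twelfth of that (2.5/29.9 = 0.08).

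**4. Are the two readings equally supported?**

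| Text | Points to |
|---|---|
| SAP 7.1.1: study treatment means either drug, with no cohort limit | not new therapy |
| Protocol 5.2.1.4: given for a possible adverse effect, patient stays on study | not new therapy |
| Protocol 7.5.1: "Chemotherapy, radiation therapy, hormonal therapy or any investigational anti-neoplastic agent for the active treatment of cancer are prohibited" | not new therapy, since the test is purpose |
| SAP 7.1.2: subsequent anti-cancer therapy is listed with end of treatment or study and death | not new therapy, since it reads as a post-treatment event |
| Protocol 4.1.2 item 5: an anti-CD20 agent combined with chemotherapy qualifies as prior B-cell lymphoma treatment | new therapy, but only weakly: an entry rule about past regimens, not rituximab alone for a virus |

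The balance is clearly towards supportive care.

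**5. Could analysts find such a case?**
Yes. SAP 7.7 codes concomitant medications from first dose to 30 days after last dose, and Protocol 11.1.3 provides response listings by patient. Appendix A of the SAP has separate date rules for concomitant medications and for subsequent anti-cancer therapy. That is consistent with the two being recorded separately, though it does not prove it.

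**The case for a change.** The best argument for a change is that one defining sentence costs almost nothing and would remove any choice made after the data are seen. The SAP 7.1.1 definition was probably written for Cohort 2, since the rituximab-related adverse event tables are restricted to that cohort. Leaning on it for EBV use in Cohort 1 would place a possibly rituximab-assisted response in a single-agent estimate without a flag. Detection does not depend on fever alone either: EBV PCR is done at screening in every patient, and the footnote in 5.2.1.4 reaches patients without symptoms. One patient can also matter at the 20-patient look, where 2/20 (10%, upper limit 31.7%) permits expansion and 1/20 (5%, upper limit 24.9%) closes the cohort.

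Part of this stands. No sentence classifies EBV rituximab, and attribution would be uncertain in any such patient. It does not carry the case for a change:

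- Writing down a classification would mostly confirm the reading the texts already favour.
- Extra PFS and DOR analyses censored at rituximab are not shown to alter any result, and that censoring may itself be informative.
- The 20-patient example needs exactly two responses, one of them following EBV rituximab. Cohort 1 was among the first three cohorts opened in Phase 2a, and the EBV section appears in the amendment table only from Amendment 7, so that look may have come first. Enrolment dates are not given.
- SAP Section 8 cites a Study Data Handling Document that is not among the documents reviewed and may already contain the rule.

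**Conclusion.** The term is undefined and a first response after EBV rituximab is possible, so the question is fair. It is nevertheless missing detail, not a faulty analysis. The texts point to one sensible reading, in which EBV rituximab does not end the response window, and any affected patient can be traced from coded medications and response listings and described in the report. The number of such patients is unknown and may be zero; the one-to-three range above is an assumption. At n = 40 each moves ORR by 2.5 points within an interval about 30 points wide. Protocol 11.1.3 sets no success criterion that such a shift could cross. The conclusion assumes that the analysts follow the purpose-based reading and apply it alike to best response, PFS and DOR. No change to the plan is needed, and EBV management is not in question.
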